Our formative qualitative work supports the use of virtual MBCT for ACS patients. We recently conducted a qualitative study (individual patient interviews) to solicit patient's perspectives and needs for a behavioral depression treatment based on MBCT. Patients were open and interested in a mindfulness program, identified a range of symptoms and needs for the intervention to target, offered suggestions for promoting videoconferencing feasibility, and expressed openness to participate in dried blood spot research procedures. The results of this formative work have been integrated into the current proposal.

This proposal is to develop an MBCT intervention adapted for ACS patients and test the feasibility and acceptability of the intervention, delivered via group videoconferencing, for ACS patients with depressive symptoms. This research will incorporate a novel, minimally invasive blood spot data collection procedure to measure inflammation. This innovative project will be one of the first to explore MBCT for ACS patients, and to test MBCT delivered via group videoconferencing. It will generate knowledge about e-health technologies and congruent research methods to apply to other mind-body interventions and patient populations.

Toward these goals, the purpose of the current study is to conduct an open pilot trial to explore the feasibility and acceptability of the adapted MBCT intervention and research procedures, to inform refinements for a future pilot RCT.

RESEARCH DESIGN AND METHODS

Briefly describe study design and anticipated enrollment, i.e., number of subjects to be enrolled by researchers study-wide and by Partners researchers. Provide a brief summary of the eligibility criteria (for example, age range, gender, medical condition). Include any local site restrictions, for example, "Enrollment at Partners will be limited to adults although the sponsor's protocol is open to both children and adults."

The current study will employ an open pilot trial to determine the initial feasibility and acceptability of a targeted, virtual MBCT intervention for ACS patients. We plan to enroll approximately N=20 patients (2 cohorts of 10 participants/per cohort, accounting for 20% anticipated lost to follow-up). The MBCT intervention will involve 8 virtually-delivered MBCT sessions (approximately 1.5 hours each), during which participants will be taught how to use evidence-based mindfulness skills to regulate distress and choose healthy behaviors, as well as

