Feasibility outcomes for recruitment include: $\geq 70\%$ of patients reached consent to screening, $\geq 70\%$ meet screening criteria, $\geq 70\%$ of eligible enroll, and enrolling approximately N=20 participants within 1-2 months. Feasibility for eligibility criteria include: $< 20\%$ ineligible due to each criterion, reasons for ineligibility, reasons for refusal, and characteristics of refusers. MBCT feasibility will be measured by: $\geq 75\%$ session attendance, $\geq 75\%$ post-assessments completed, $\geq 70\%$ follow-up assessments completed, fidelity checklist score $\geq 80\%$, and $\geq 75\%$ complete home practice at least 3 days/week. Videoconferencing feasibility will be assessed by: $< 20\%$ of connections dropped during session; $< 20\%$ of sessions missed due to technical problems; number (Mean < 2.0) and types of problems, $< 20\%$ ask for extra training and type of extra training needed. Blood spot feasibility will be assessed by $\geq 75\%$ of samples submitted at baseline and post-intervention, $\geq 60\%$ submitted at follow-up, and 80% of samples of adequate quality.

Acceptability outcomes will be assessed via post-session surveys, post-intervention surveys, and exit interviews. MBCT acceptability will be assessed by average scores ≥ 7.5 on ratings of session helpfulness, enjoyment, relevance, and utility of session components (scale of 1 = not at all to 10 = very much). Overall program satisfaction will be assessed by $M \geq 7.5$ regarding overall program satisfaction, $\geq 75\%$ of participants reporting that they plan to use the skills in the future, $\geq 75\%$ reporting that they would recommend the program to others, and $\geq 60\%$ reporting continued mindfulness practice on the follow-up survey. Likes and dislikes will be explored in the exit interviews. Videoconferencing acceptability will be assessed in terms of ease and

confidence of use (1 = not at all to 10 = extremely, $M \geq 7.5$), interference of technical problems (1 = none to 10 = extreme, $M < 2.0$), audiovisual quality and overall satisfaction (1 = poor to 10 = excellent, $M \geq 7.5$), and themes related to pros and cons and suggestions for improvement in the exit interviews. Blood spot acceptability will be assessed by ratings of ease of data collection and submission (1 = not at all, 10 = extremely; $M \geq 7.5$), level of pain (1 = none, 10 = extreme, $M < 2.0$), and concerns and suggestions for improvement expressed in the exit interview.

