Regarding survey data, a member of study staff will verify that all items on all questionnaires have been addressed. Data will be checked for out of range values using frequency distributions prior to analyzing the data. For blood spot samples, our collaborators at Northwestern University will inform us of the number of samples that were not of adequate quality for analysis and the participant ID numbers of these samples. The Principal Investigator will be responsible for ensuring compliance with IRB procedures.

For guidance, refer to the following Partners policies:

Data and Safety Monitoring Plans and Quality Assurance

<https://www.partners.org/Assets/Documents/Medical-Research/Clinical-Research/DSMP-in-Human-Subjects-Research.pdf>

Reporting Unanticipated Problems (including Adverse Events)

<https://www.partners.org/Assets/Documents/Medical-Research/Clinical-Research/Reporting-Unanticipated-Problems-including-Adverse-Events.pdf>

PRIVACY AND CONFIDENTIALITY

Describe methods used to protect the privacy of subjects and maintain confidentiality of data collected. This typically includes such practices as substituting codes for names and/or medical record numbers; removing face sheets or other identifiers from completed surveys/questionnaires; proper disposal of printed computer data; limited access to study data; use of password-protected computer databases; training for research staff on the importance of confidentiality of data, and storing research records in a secure location.

NOTE: Additional measures, such as obtaining a Certificate of Confidentiality, should be considered and are strongly encouraged when the research involves the collection of sensitive data, such as sexual, criminal or illegal behaviors.

In terms of risks to privacy, there is an inherent risk in the discussion-based group intervention format. There is a risk of a participant sharing personal information gathered from the groups

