## 6. DATA ANALYSIS

**6.2. Aim 2: Open pilot trial.** This is a small, single-arm, pilot feasibility trial to establish preliminary feasibility and acceptability of the intervention to inform intervention adaptations for a future randomized trial. This is not a randomized clinical trial to explore efficacy of treatment on outcomes. As such the analyses are focused on descriptive statistics. Frequencies and proportions will be calculated to assess feasibility outcomes. Feasibility outcomes are: recruitment feasibility (percent of participants who consent to screening; percent of participants meeting screening criteria; percent of eligible patients who consent); MBCT feasibility (percent of participants adherent to the MBCT intervention; percent of participants retained at post-intervention); videoconferencing feasibility (percent of connections dropped during sessions); and blood spot feasibility (percent of blood spot sample completion at baseline; percent of blood spot sample completion at post-intervention; percent of blood spot samples completed at follow-up; percent of adequate blood spot samples submitted). Means and standard deviations or medians and interquartile ranges will be calculated to assess acceptability ratings. Acceptability outcomes are rated from 0-10 with higher scores indicating greater acceptability and consist of: MBCT acceptability (helpfulness for mood; usefulness of session components); videoconferencing acceptability (ratings of videoconferencing ease of use; ratings of videoconferencing quality surveys; ratings of videoconferencing satisfaction); and blood spot acceptability (ease of blood spot collection; discomfort of blood spot collection).

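### Blood-spot submission and adequacy are never combined within a participant, so every benchmark can be met while well under 75% of enrolled participants have usable samples both before and after the intervention

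*Protocol*

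**What the plan says.** Feasibility of the dried blood spot procedures is part (c) of the protocol's Specific Aim 1. Samples for IL-6, CRP and TNF-alpha are to be self-collected before the intervention, after it, and 3 months later (Research Design and Methods, dried blood spots).

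The measured-outcomes text of the same section gives the benchmarks: at least 75% "of samples submitted at baseline and post-intervention", and at least 60% "submitted at follow-up, and 80% of samples of adequate quality". Submission is therefore tied to time points. Adequacy is a single figure, "80% of samples of adequate quality", with no time point and no stated denominator.

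SAP section 6.2 follows the same pattern. Completion has a separate entry for each time point, for example "percent of blood spot sample completion at post-intervention", while adequacy has one entry, "percent of adequate blood spot samples submitted". Neither document has a measure that links a participant's samples across time points.

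Three other provisions matter:

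- Participants may decline any single collection (Research Design and Methods, minimisation of risks).
- Under Monitoring and Quality Assurance, the laboratory will report "the number of samples that were not of adequate quality for analysis and the participant ID numbers of these samples".
- Each sample sent to the laboratory is labelled with participant ID and time point (Sending Specimens/Data to Research Collaborators Outside Partners).

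**The concern.** A sample is useful for measuring change only if it arrives, can be assayed, and has a usable counterpart from the same person at the other time. The plan scores arrival and quality as separate marginal rates and never asks how many people have both. A reader who sees 75% submission and 80% adequacy may assume that about three quarters of participants have before-and-after data. The actual share could be much lower, and the planned summaries would not show it.

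The single adequacy figure could also hide a fall in quality after baseline. Collection guided by the research assistant is described only before the intervention starts. Supported collection at the hospital is available if needed, but no routine guided session is described later. Late-arriving samples are requested again, but no replacement is described for samples the laboratory finds inadequate.

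At stake is how well Aim 1(c) informs the next study. The background names these three cytokines as treatment targets, so whether home collection yields pre-post data is a natural question for the subsequent pilot RCT.

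**Working it through.** **Inputs.** Enrolment: "We plan to enroll approximately N=20 patients (2 cohorts of 10 participants/per cohort", so 2 × 10 = 20, which reproduces the plan's figure. The protocol adds "accounting for 20% anticipated lost to follow-up"; 16 / (1 − 0.20) = 20 is consistent, although 16 completers is inferred, not stated. The blood-spot benchmarks have no derivation to reproduce.

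**Assumptions.** Submission percentages are of the 20 enrolled. Adequacy is of samples submitted, pooled over time points. The documents state neither.

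**Every benchmark just met**

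- Submitted: 0.75 × 20 = 15 at baseline, 15 at post-intervention, and 0.60 × 20 = 12 at follow-up; total 42.
- Adequate: 0.80 × 42 = 33.6, so at least 34. Up to 42 − 34 = 8 may be inadequate.

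**Usable baseline-post pairs**

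| Pattern | Calculation | Pairs of 20 |
|---|---|---|
| Submission and adequacy independent | 0.75² × 0.80² = 0.36 | 7.2 |
| Same 15 submit twice, adequacy independent | 0.75 × 0.80² = 0.48 | 9.6 |
| Same 15 submit twice, adequacy fully consistent within person | 0.75 × 0.80 = 0.60 | 12 |
| Lower bound: fewest double submitters, each failure in a different pair | (15 + 15 − 20) − 8 | 2 |
| Upper bound: same 15 submit twice, all 8 failures at follow-up | 15 − 0 | 15 |

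Placing exactly 8 failures at random among the 42 samples gives much the same means. The chance that both samples of a pair are adequate is (34/42) × (33/41) = 0.652. Expected double submitters are 15 × 15/20 = 11.25 with random overlap, giving 7.3 pairs, or 15 with the same submitters, giving 9.8.

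**Can the planned percentages recover the number?** No. The product 0.75 × 0.80 = 0.60 is an average usable rate per time point (0.60 × 0.80 = 0.48 at follow-up), and only if failures are spread evenly. It does not show who supplied both samples. If the same 15 people submit twice and all 8 failures are at post-intervention, adequacy there is 7/15 = 47% and 7 pairs remain, yet every benchmark passes.

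**How much is due to the unsplit adequacy figure?** Requiring 80% at each time point gives 0.80 × 15 = 12 adequate at baseline and 12 at post-intervention. The lower bound rises only from 2 to 12 + 12 − 20 = 4, or from 7 to 15 − 3 − 3 = 9 with the same submitters. Splitting adequacy helps, but the larger cause is the lack of any within-person count.

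**Other readings**

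- If the 75% benchmark means that 75% of participants submit at both times, the lower bound at the thresholds is 15 − 8 = 7.
- If adequacy is of all 60 expected samples, 0.80 × 60 = 48 must be adequate. That exceeds the 42 submitted at the thresholds, so submission would have to be higher. At most 12 person-time slots are then unusable, and the lower bound is 20 − 12 = 8.

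Both readings reduce the problem without removing it.

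**The case against.** The strongest reply is that this is a small descriptive pilot, that separate rates are useful, and that nothing is lost. Unwillingness to submit and poor collection technique call for different refinements, and separate measures tell them apart. Because samples carry ID and time point, paired rates could be tabulated later. All of this stands. It is why the existing measures should stay, and it makes this a reporting gap, not a design failure.

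The lower bound of 2 is also contrived. It needs five people who submit only at baseline, five who submit only at post-intervention, and all 8 failures in different pairs. With random overlap and random failures its probability is (3,003 / 15,504) × (45 × 2⁸ / 118,030,185), about 0.002%. Baseline submitters are likely to make up most post-intervention submitters, which favours the 10 to 12 range over 7.

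A reader might infer three stronger things that the documents do not support:

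- **That there would be far too few pairs.** No required number of pairs, standard deviation or effect size is given for any marker.
- **That passing the benchmarks would carry the procedure forward automatically.** There is no go/no-go rule; the stated purpose is to inform refinements for a pilot RCT.
- **That a later trial must have complete pairs.** Likelihood-based longitudinal models can use a participant with one sample, although pairs are more informative about change.

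Pooling of adequacy over time is itself an inference from the missing time point and the single SAP entry.

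**Conclusion.** The point holds as a gap in what the feasibility measures show. Meeting every benchmark is compatible with about 7 to 12 of 20 participants (36% to 60%) having usable baseline-post pairs under ordinary patterns, with 2 and 15 as extreme bounds when each benchmark is just met. The planned percentages cannot show which applies.

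The figures rest on 20 enrolled as the denominator for submission and on submitted samples as the denominator for adequacy. The alternative readings raise the lower bound to 7 or 8 but still leave it well below 75%. A drop in quality after baseline is a possibility that the single figure could conceal; nothing in the documents predicts one.

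The consequence is confined to judging whether home blood spots can supply pre-post inflammation data in the subsequent pilot RCT. It should not be read as a threat to an efficacy result in this trial: the SAP is descriptive, and the secondary outcomes correspond to the self-report surveys, not to change in inflammatory markers.

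**What to change.** Keep the existing submission and adequacy measures. Add to the protocol's measured outcomes and to SAP section 6.2, with all enrolled participants as the denominator:

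- (a) the percent with an adequate sample at each time point;
- (b) the percent with adequate samples at both baseline and post-intervention, and the percent with adequate samples at both baseline and follow-up.

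State the denominators of the existing percentages at the same time. Base the blood-spot feasibility conclusion on the new measures alongside the present benchmarks. The documents supply no threshold for the paired measure, so the team should either set one before looking at the data or say that it is reported descriptively.

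The cost is a few extra percentages from labels and laboratory reports already planned, with no new visits, samples or participant burden. The downside is a headline rate less favourable than either marginal figure.

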Post-session surveys. The post-session surveys will be administered immediately after each of the 8-sessions and will assess participants' perceptions, and likes and dislikes, of specific intervention components. Prior to each session participants will be asked to email, mail, or complete via REDCap a record of their at-home mindfulness practice since the previous session. The post-session surveys and home practice log are included in the IRB submission.

Exit interview. Upon completion of the intervention, participants will be asked to complete a 30-60 minute exit interview via phone or video conference. These interviews will be audio- and/or video-recorded for transcription.

Dried blood spots. Within one week before and after the intervention and 3-months-post intervention, participants will be asked to provide self-collected whole dried blood spots to assess IL-6, CRP, and TNF- α using a minimally invasive finger skin prick technique, which involves pricking the finger with a lancet, milking the finger to produce 5-10 drops of blood onto filter paper, allowing the blood spots to dry, and mailing it to the study team at MGH in a secure envelope. Prior to the start of the intervention, an RA will guide the participant in self-collecting blood samples via a videoconference call, phone call, and/or in person (per the participant's preference). Participants will be sent a video link for a guided demonstration of the procedure and/or written instructional handouts. The RA will ask the participant a series of questions to gauge understanding, provide corrective feedback, and answer any questions the participant might have before proceeding to guide the participant in the procedure. Skin prick procedures are safe for patients on beta-blockers and anticoagulants. Participants may also receive written instructional materials.

Participants will be asked to allow the sample to dry overnight, document the date the sample was taken on the filter paper, and mail it to the study team at MGH the next morning. Samples

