As the intervention is psycho-educational in nature, and participants do not need to physically come to the hospital to participate in any study procedures, there is no risk of physical injury to participants. There is a risk of mild, temporary physical discomfort due the blood spot procedures, which will be handled as described above. The blood spot finger-prick technique is safe for ACS patients. Participation is voluntary for all subjects. As explicitly stated in the informed consent documents, participants may withdraw from participation at any time by notifying study staff. Participants will not be required to provide a reason for withdrawal. Participants will be reminded that they can withdraw from the study at any point during their participation.

The main psychosocial safety concern related to patients in this study is worsening depression symptoms and/or suicidal ideation. Subject safety regarding mood and suicidal ideation will be ensured in several ways.

First, eligibility criteria require that patients do not have active suicidal ideation at the time of enrollment, and that they have not been hospitalized for a psychiatric reason in the past year. Thus, it is not likely that participants will report suicidal ideation during or following the intervention. Moreover, our eligibility criteria require only minimal depression symptoms and thus we do not expect to have a severely depressed sample.

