During the eligibility screening procedures, participants will be administered the Patient Health Questionnaire-9 (PH-9) over the phone. If any patient endorses suicidality (i.e., PHQ-9 item 9 score above 0; “Over the past two weeks, how often have you been bothered by thoughts that you were better off dead or of hurting yourself in some way”), the RA will follow our standardized, published safety assessment protocol that our team has developed and used in prior funded studies of ACS patients with elevated depression symptoms. The protocol involves further assessing safety risks through a series of structured questions, with specific instructions at each step based on the patients’ response. It begins by clarifying the response to PHQ-9 item 9 (i.e., determining passive versus active suicidality). If patients endorse active suicidality, the RA will further assess safety risks (e.g., plan, intent, past suicide attempts) and immediately notify the PI (a licensed clinical psychologist) to conduct further assessment. The RA will attempt to keep the patient on the phone until the PI has reached them. The PI will conduct detailed suicide assessment of patients with active suicidality and inform the patient’s primary treatment providers of the patient’s symptoms and assist with the obtainment of further evaluation and care as needed (e.g., through referral to outpatient treatment or to the emergency department [ED]), depending on the urgency of the situation. In our previous work, it has been extremely rare for an ACS patient to report active suicidality that requires intervention.

Upon enrollment, the RA will also conduct proactive safety planning with all participants in the following ways: (1) asking participants to identify 1-2 safety contacts that we would contact in the event that participants become at risk, (2) working with participants to identify the emergency department nearest to their home; (3) and instructing patients to go to this emergency room if they feel unsafe, and inform research staff once they are in a safe place (e.g., hospitalized or back at home). Participants will be asked to report any worsening symptoms to the interventionist during sessions, or in between sessions by contacting the study RA.

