For enrolled participants, the PHQ-9 will be administered at baseline, post-intervention, and 3-month follow-up, which will allow us to monitor for worsening depression symptoms. The RA will review changes in participant’s PHQ-9 scores over time and contact the participant to discuss any concerns, asking about their symptoms, needs, and concerns about staying in the study, and conducting an initial safety assessment as needed (as described above). The same procedures as described above will be followed if participants endorse suicidality on PHQ-9 item 9 when completing the measure as part of any of the surveys. REDCap will be set up to send automatic alerts to the study staff for any PHQ-9 item 9 responses greater than zero. Participants will be contacted within 24 hours.

The interventionists will observationally monitor participant’s symptoms during each weekly intervention session. If the interventionists become concerned based on a participant’s presentation during a session (e.g., per their clinical observation or expressed SI by a

participant), they will call the participant by phone individually immediately after the session to check in about the participant's symptoms and conduct a safety assessment if needed (following the protocol outlined above). The interventionist will be a licensed mental health provider trained in conducting safety assessments. Interventionists will instruct patients at the start of the first session, and periodically remind them throughout the intervention, that if they experience suicidal thoughts or worsening depression symptoms at any point during the study, they should let the interventionist, study staff, and/or their doctors know.

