Describe the plan for monitoring the data to ensure the safety of subjects. The plan should include a brief description of (1) the safety and/or efficacy data that will be reviewed; (2) the planned frequency of review; and (3) who will be responsible for this review and for determining whether the research should be altered or stopped. Include a brief description of any stopping rules for the study, when appropriate. Depending upon the risk, size and complexity of the study, the investigator, an expert group, an independent Data and Safety Monitoring Board (DSMB) or others might be assigned primary responsibility for this monitoring activity.

NOTE: Regardless of data and safety monitoring plans by the sponsor or others, the principal investigator is ultimately responsible for protecting the rights, safety, and welfare of subjects under his/her care.

The principal investigator is ultimately responsible for data and safety monitoring. If study staff become aware of any adverse events, the event will be reported immediately to the PI. All data will be entered into a password protected database and cleaned for accuracy. Electronic participant tracking databases will be stored on a secure server. Data collected using REDcap will identify patients only by study ID. The main safety risks for the study include the potential for psychological discomfort with surveys.

Describe the plan to be followed by the Principal Investigator/study staff for review of adverse events experienced by subjects under his/her care, and when applicable, for review of sponsor safety reports and DSMB reports. Describe the plan for reporting adverse events to the sponsor and the Partners' IRB and, when applicable, for submitting sponsor safety reports and DSMB reports to the Partners' IRBs. When the investigator is also the sponsor of the IND/IDE, include the plan for reporting of adverse events to the FDA and, when applicable, to investigators at other sites.

NOTE: In addition to the adverse event reporting requirements of the sponsor, the principal investigator must follow the Partners Human Research Committee guidelines for Adverse Event Reporting

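### Apart from PHQ-9 mood and suicidality monitoring, the plan describes no systematic adverse-event inquiry, so other events may be under-ascertained, especially in non-attenders and during follow-up

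*Protocol*

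**What the plan says.** The Protocol deals with safety in three places.

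- **Data and Safety Monitoring.** The general rule is "If study staff become aware of any adverse events, the event will be reported immediately to the PI". The investigator then judges relatedness for serious and non-serious events and reports to the IRB. On risk, the section says "The main safety risks for the study include the potential for psychological discomfort with surveys".
- **Research Design and Methods, on ensuring subject safety.** Here "The main psychosocial safety concern related to patients in this study is worsening depression symptoms and/or suicidal ideation". For that concern the procedures are specific: "the PHQ-9 will be administered at baseline, post-intervention, and 3-month follow-up, which will allow us to monitor for worsening depression symptoms"; the RA reviews score changes; and "REDCap will be set up to send automatic alerts to the study staff for any PHQ-9 item 9 responses greater than zero", with contact within 24 hours. Interventionists also observe participants' "symptoms during each weekly intervention session". In addition, "Participants will be asked to report any worsening symptoms to the interventionist during sessions, or in between sessions by contacting the study RA".
- **Monitoring and Quality Assurance.** Adverse events are discussed at the weekly team meeting.

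The scheduled data collection is described under Data collection, Survey measures and Post-session surveys. The three batteries consist of named scales plus items on expectancy, group cohesion, satisfaction, continued practice and COVID-19. The post-session survey covers "perceptions, and likes and dislikes, of specific intervention components". The log records home practice. Health-record extraction is for medical and demographic variables. SAP section 6.2 lists descriptive feasibility and acceptability summaries and no adverse-event summary.

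**The concern.** How completely adverse events are counted depends on how they are looked for. A rule that begins when staff learn of an event says what happens next, but not how staff come to learn of it. The later steps (relatedness review, IRB reporting, weekly discussion) also act on events already known.

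Participants have a lifetime history of acute coronary syndrome and are aged 35 to 85. The Protocol's background links depression in such patients to further cardiac events and readmission. Medical events during about five months of participation are therefore foreseeable, and a PHQ-9 will not record them. The investigator's duty to review every event, serious or not, cannot be met for events nobody asks about. A low count at the end could reflect few events or little inquiry, and the plan gives no way to tell which.

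**Working it through.** The documents state no adverse-event rate, count or safety power, so there is no planned figure to reproduce. The check is a comparison of what is asked, and when, followed by simple arithmetic for scale.

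**What each contact asks about**

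| Contact | Timing | Reaches non-attenders? | Mood or suicidality | Other adverse events |
|---|---|---|---|---|
| PHQ-9 in the batteries | Baseline, post-intervention, 3 months | Yes | Yes, with item 9 alert | No |
| Other battery items | Same | Yes | Some scales | None described |
| Post-session survey | After each of 8 sessions | Not stated | Not described | None described |
| Practice log | Before each session | Not stated | No | None described |
| Interventionist observation | Weekly | No | Yes | Only if raised or noticed |
| Participant reports to staff | Any time | Yes, if the participant makes contact | Yes | Worsening symptoms, unprompted |
| Exit interview | End of intervention | If completed | Not described | Likes, dislikes, blood-spot concerns |
| Record extraction | Not stated | Yes | Not stated | No stated purpose |

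No row contains a fixed-time question on other adverse events.

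**Scale of the unobserved part**

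Inputs from the Protocol: about 20 participants, 8 weekly sessions, and benchmarks of at least 75% attendance, 75% post-intervention completion and 70% follow-up completion.

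- Participant-sessions: 20 × 8 = 160. Missed at exactly 75% attendance: 0.25 × 160 = 40.
- No post-intervention survey at exactly 75%: 0.25 × 20 = 5 participants.
- No 3-month survey at exactly 70%: 0.30 × 20 = 6 participants.
- Time without weekly sessions, assuming 13 weeks to follow-up: 13 / (8 + 13) = 13/21 = 62%. Assuming 12 weeks: 12/20 = 60%.

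These figures measure missed contact and not missed events.

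**What incomplete capture would do (illustration)**

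Suppose each participant has a 10% risk of an event and a fraction c of events is captured. Both are assumptions, since the documents give neither. The chance of recording at least one event among 20 is 1 − (1 − 0.10c)^20.

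| c | Expected number recorded (20 × 0.10 × c) | Chance of recording at least one |
|---|---|---|
| 1.00 | 2.0 | 88% |
| 0.75 | 1.5 | 79% |
| 0.50 | 1.0 | 64% |
| 0.25 | 0.5 | 40% |

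On these assumptions, halving capture raises the chance of an empty table from 12% to 36%.

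**The case against.** The strongest reply is that the harm the Protocol worries about most is well covered. The PHQ-9 is scheduled three times whatever the attendance, its suicidality item triggers an alert and prompt contact, and participants are told to report worsening at any time. They also name safety contacts and are asked to inform staff after an emergency visit made because they felt unsafe. All of this stands. A reader might infer from the conditional rule that every event in non-attenders or during follow-up is lost; for mood and suicidality the documents show otherwise.

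Four further replies carry weight.

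- The conditional sentence governs escalation to the investigator and does not limit what may be recorded. That is right. The gap is that no other text supplies the inquiry.
- The survey forms and the log went to the IRB and are not among the documents, so an adverse-event item may exist. The SAP is also an excerpt. The point is therefore confined to what is described.
- Some contact is left out of a sessions-and-surveys count. Blood-spot pain is rated, concerns about the procedure are sought in the exit interview, and there is a 3-month blood sample with contact over its receipt. These soften the gap for finger-prick problems, but none is described as asking about cardiac events or admissions.
- The two risk statements are not strictly contradictory. The monitoring section says the main risks include survey discomfort, which leaves room for others. It is incomplete, because it omits the concern on which the safety section is built.

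**Conclusion.** The point holds in a limited form. Mood and suicidality are actively monitored. For other adverse events the described plan has no fixed-time inquiry, no collection window and, in the SAP text available, no summary. Under-ascertainment is therefore possible, and most likely among participants who miss sessions and in the roughly 60 to 62% of participation after the last session (assuming 12 to 13 weeks to follow-up). How many events would be missed cannot be derived from the documents.

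Three stronger conclusions are tempting and should not be drawn.

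- That participants who stop attending are the ones worsening: plausible, but undocumented.
- That undercounts would bias the later randomised trial: the documents say this pilot passes on feasibility and acceptability refinements, and do not say that event counts are carried forward.
- That an upper confidence limit for zero events among 20 measures the problem: that limit reflects the sample size and would be the same with complete capture.

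This is an inexpensive improvement to a small single-arm pilot and does not undermine its primary feasibility aims.

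**What to change.** 1. Add one fixed question on new or worsening symptoms, emergency visits and hospital admissions since last contact. Put it in the existing weekly practice log or post-session survey, sent to all participants whether or not they attended, and in the post-intervention and 3-month batteries. If the forms already contain such an item, say so in the Protocol.
2. State the collection window, for example consent to the 3-month assessment, and add hospital visits within it to the existing record extraction. This also gives some information on participants who return no survey.
3. Add a descriptive adverse-event table to the SAP, separating the intervention and follow-up periods and showing seriousness and relatedness. The weekly meeting already provides the forum for review.
4. Reconcile the list of main safety risks under Data and Safety Monitoring with the concern named in the subject-safety text.

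The cost is one survey item, a few record fields and one table, with no extra visits. The downside is more minor events to log and review.
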